Primary Study Evaluations	
1. Procedural success defined as completing the planned procedure without femoral access bailout2. Technical success defined as delivery of HydroPearl to the target vessel and slowing the blood flow with microsphere embolization.3. Freedom from Major Adverse Events within 30 days of procedure, defined as:
a. Deathb. MIc. Stroke4. Freedom from radial access related complications at 30 days, defined as:
a. Radial artery occlusion (reverse Barbeau and/or Ultrasound, per site standard of care)b. Hand ischemiac. Arteriovenous fistulad. Pseudoaneurysme. Any complication requiring surgical and/or endovascular intervention within 30 days of index procedure
Additional Evaluations	
1. Incidence of Radial Artery Occlusion Complications at any time
a. Arteritis

	
b. Cellulitisc. Ecchymosisd. Pain at puncture sitee. Hematoma 
2. Quality of Life and Health Economics3. Procedural endpoints:
a. Blood lossb. Patient radiation exposurec. Contrast volumed. Time to hemostasise. Total procedural timef. Time to dischargeg. Operative timeh. Radial cocktail components and frequency of administration4. Access endpoints:
a. Radial artery spasmb. Time to dischargec. Radial access pain VAS5. Closure endpoints
a. Time to hemostasisb. Time to ambulation
Procedure Evaluations	
1. Tumor type2. Number and size of tumors / fibroids3. Post embolization syndrome4. UFE:
a. If post-op MRI is obtained per standard of care: Effectiveness of HydroPearl measured by MRI.
i. Infarction is characterized by complete (100%), 90-99%, 50-89%, or less than 50%.ii. Uterine Volumeiii. Dominant Fibroid Volumeb. EQ-5Dc. UFS-QoLd. Return to normal activitiese. Pain VASf. Symptoms including bleeding and bulkg. Pregnancy intention and occurrence5. Prostate Artery Embolization:
a. IPSS with Quality of Lifeb. EQ-5Dc. Return to normal activitiesd. Pain VAS

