2.3 Study Duration

Study enrollment is expected to occur over an 18-month period. Follow-up will continue for each subject through 365-days post-procedure.

3 Study Objective and Evaluations

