3.2.1 Primary Evaluations

Primary Safety Evaluation:

The primary safety evaluation is freedom from major adverse events and radial access complications within 30 days post-procedure.

Major Adverse Events are defined as:

1. Death
2. MI
3. Stroke

Radial Access related complications are defined as:

1. Radial artery occlusion
2. Hand ischemia
3. Arteriovenous fistula
4. Pseudoaneurysm
5. Any complication requiring surgical and/or endovascular intervention within 30 days of index procedure.

Primary Efficacy Evaluation:

The primary efficacy evaluations are procedural success and technical success.

1. Procedural success is defined as completing the planned procedure without femoral access bailout.
2. Technical success is defined as delivery of HydroPearl to the target vessel and slowing the blood flow with microsphere embolization. Embolization may be confirmed clinically or radiologically at the discretion of the site investigator.

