3.2.2 Additional Evaluations

Additional evaluations include:

1. Incidence of Radial Artery Occlusion Complications at any time
 - a. Arteritis
 - b. Cellulitis
 - c. Ecchymosis
 - d. Pain at puncture site
 - e. Hematoma

2. Quality of Life and health economics
3. Post embolization syndrome
4. Procedural endpoints:
 - a. Blood loss
 - b. Patient radiation exposure
 - c. Contrast volume
 - d. Time to hemostasis
 - e. Total procedural time
 - f. Time to discharge
 - g. Operative time
5. Access endpoints:
 - a. Radial artery spasm,
 - b. Time to discharge
6. Closure endpoints
 - a. Time to hemostasis
 - b. Time to ambulation
7. Tumor type
8. Number and size of tumors / fibroids
9. Post embolization syndrome
10. UFE:
 - a. If post-op MRI is obtained per standard of care: Effectiveness of HydroPearl measured by MRI.
 - i. Infarction is characterized by complete (100%), 90-99%, 50-89%, or less than 50%.
 - ii. Uterine Volume
 - iii. Dominant Fibroid Volume
 - b. EQ-5D
 - c. UFS-QoL
 - d. Return to normal activities
 - e. Pain VAS
 - f. Symptoms including bleeding and bulk
 - g. Pregnancy intention and occurrence
11. PAE:
 - a. IPSS with Quality of Life

- b. EQ-5D
- c. Return to normal activities
- d. Pain VAS
- e. Qmax
- f. Prostate volume

12. Liver Tumor Embolization:

- a. Tumor response (mRECIST - CR, PR, SD, PD)
- b. EQ-5D
- c. Return to normal activities
- d. Pain VAS
- e. Disease stage

13. Other Hypervascular Tumors

- a. Infarction
- b. Tumor Response (mRECIST – CR, PR, SD, PD)
- c. Return to normal activities
- d. Pain VAS

14. Arteriovenous malformations:

- a. EQ-5D
- b. Return to normal activities
- c. Pain VAS

4 Study Design

This is a prospective, multi-center, registry study to assess the procedural success, technical success, and complication rate of radial access procedures using HydroPearl microspheres.

A subject is considered enrolled into the study once the guidewire is inserted into the radial artery.

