7.2 Procedure

Subjects that meet the eligibility criteria and have signed the informed consent will have their scheduled procedure performed in accordance with investigator/site standard practices. Any on-label use of HydroPearl microspheres are permitted this study; that is, treatment of arteriovenous malformations and hypervascular tumors including uterine fibroids.

Table 2: Schedule of Events

Assessment	Screening / Baseline	Procedure	Discharge	30 Day Follow-up ±14 days	180 Day Follow-up ±30 days	365 Day Follow-up ±30 days
Informed Consent	X					
Eligibility Criteria	X					
Medical History/Demographics	X					
Pregnancy Test [¶]	X					
Blood Tests, including platelets and INR (if available) *	X	X	X	X	X	X
Embolized target organ Imaging (if available)	X	X	X	X	X	X
Physical Exam	X	X	X	X	X	X
Procedure, Access, Closure Evaluations		X				
Quality of Life questionnaires and return to normal activities	X		X	X	X	X
Concomitant Medications (Intra-op and Anticoagulation / Antiplatelets Only)	X	X	X	X		
Device Related Adverse Events ^{§§}		X	X	X	X	X

[¶] Pregnancy test if female of child-bearing potential (collected prior to procedure according to site standard of care)

* Blood Tests include Complete Blood Count (CBC), Platelet Count, Serum Creatinine, Hemoglobin (HGB), Blood Urea Nitrogen (BUN), Hematocrit (HCT) and Prothrombin time/INR, only as collected per standard of care

^{§§} Device related adverse events should be recorded during the entire course of the study from time of enrollment through end of 180 Day Follow-up visit.

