13.2.1 Study Visit

The Study Visit Day 0 is the date of the index procedure. Day in study will be calculated relative to the index procedure as follows:

$$\text{Study Day} = \text{Assessment Date} - \text{Index Procedure Date}$$

For each subject, duration in study will be based on last study contact date which is the latest date of all follow-up visits, assessments, adverse event onset or resolution, and study exit including date of death.

Duration variables will be calculated as follows:

$$\text{Duration Days} = \text{End Date} - \text{Start Date}$$

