13.5 Handling of Missing Data

All data will be collected when possible to limit the amount of missing data. Site study coordinators will work with the site principal investigator to collect accurate patient data. The number of missing data will be reported. Only observed cases will be considered.

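### All-cause death after day 30 is not a listed evaluation, and the observed-cases rule leaves late tumor response and liver EQ-5D describing only survivors with data

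*Combined protocol and SAP*

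**What the plan says.** **Death as an outcome.** Section 3.2.1 states: "The primary safety evaluation is freedom from major adverse events and radial access complications within 30 days post-procedure". Death is one of the three major adverse events. The Study Synopsis sets the same limit: "Freedom from Major Adverse Events within 30 days of procedure, defined as".

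**Length of follow-up.** Section 2.3: "Follow-up will continue for each subject through 365-days post-procedure". Table 2 in Section 7.2 schedules "Quality of Life questionnaires and return to normal activities" and "Embolized target organ Imaging (if available" at days 180 and 365 as well as earlier. Section 7.6.4 allows the day-365 contact to be by telephone.

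**Tumor evaluations.** Section 3.2.2 item 12 (liver) lists "Tumor response (mRECIST - CR, PR, SD, PD", EQ-5D, return to activities, pain and disease stage. Item 13 (other hypervascular tumors) lists infarction, tumor response, return to activities and pain, but not EQ-5D. Neither item, nor items 6 and 7 of the synopsis Procedure Evaluations, names mortality or survival. Section 13.2 makes liver procedures, benign and malignant, a subgroup.

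**Analysis rules.** Section 13.3 bases the analyses on eligible, enrolled subjects who were treated. Section 13.5 adds: "Only observed cases will be considered". Section 13.2 plans Kaplan-Meier for time-to-event endpoints without naming a survival endpoint. Section 13.2.1 uses the date of death only to fix the last contact date, which is "the latest date of all follow-up visits, assessments, adverse event onset or resolution, and study exit including date of death".

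**Adverse events.** Section 8 collects only events rated at least possibly related to a sponsor device.

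**The concern.** A death between day 31 and day 365 from progression of liver cancer falls outside the 30-day safety evaluation. If it is not rated at least possibly device-related, it falls outside adverse event collection too. At visits after the death there is no response category and no EQ-5D value, and the observed-cases rule takes the subject out of the denominator. Such values are not missing in the ordinary sense, because none exists to be collected.

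The most unfavorable result therefore leaves the late tumor summaries instead of counting against them, and no listed evaluation reports it elsewhere. The registry tests no hypothesis, so descriptive percentages and means are its whole output. A denominator limited to survivors, and not labeled as such, passes straight into the reported result.

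**Working it through.** **The plan's own figure.** The only probability in the statistical section concerns sample size (13.1): more than 80% chance of seeing at least one major complication with 100 patients at a 1.6% rate. It reproduces: 1 − (1 − 0.016)^100 = 0.8007. It says nothing about mortality after day 30.

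**Tracing one subject through the text.** Take a liver tumor subject who dies at day 90 of progressive disease, in the investigator's view unrelated to the device.

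- Primary safety (3.2.1): not counted, because day 90 is past day 30.
- Adverse events (Section 8): not collected, because not device-related.
- Response at day 30: if imaged then, the subject has a category, possibly PD, and is an observed case at that visit.
- Response and EQ-5D at days 180 and 365: no value, so dropped under 13.5.
- Date of death: used for duration in study (13.2.1), not for a survival estimate.

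Section 3.2.2 gives no time point for tumor response. Days 180 and 365 follow from the imaging schedule in Table 2, and 13.2.2 analyzes assessments by the visit entered.

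**Size, on assumed inputs.** The documents give no number of tumor subjects, response rate or mortality. Let r be the response rate among survivors and m the proportion who die before the visit. Suppose every survivor is assessed, so that only deaths are at issue.

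- Observed-case rate = r
- All-treated rate, death counted as non-response = r × (1 − m)
- Difference = r × m

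| m | All-treated rate, r = 40% | Difference (points) | All-treated rate, r = 60% | Difference (points) |
|---|---|---|---|---|
| 5% | 38% | 2 | 57% | 3 |
| 10% | 36% | 4 | 54% | 6 |
| 20% | 32% | 8 | 48% | 12 |
| 40% | 24% | 16 | 36% | 24 |

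**Would a late death be likely at all?** The chance of at least one among n liver subjects is 1 − (1 − m)^n, again with n and m assumed:

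| n | m = 5% | m = 10% | m = 20% |
|---|---|---|---|
| 10 | 40% | 65% | 89% |
| 20 | 64% | 88% | 99% |

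Even a small subgroup with modest mortality would probably meet the problem.

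**The case against.** The strongest reply is about scope. The objective is technical and procedural success and complication rates with radial access. The primary evaluations are procedural or end at day 30, and no one-year survival or oncologic claim is made. On that view, adding mortality adds an endpoint and corrects no error. It is true that no primary result changes. But the plan itself chose to follow malignant liver cases for a year and to report response and EQ-5D, and its stated missing-data rule determines whom those summaries describe.

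Four stronger readings are tempting, and the documents do not support them.

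- *Late deaths are recorded nowhere.* A death at least possibly device-related is reportable to day 365 under Section 8. (The Table 2 footnote stops at the 180-day visit, and the two must be reconciled.) Date of death enters duration in study, Section 5.7 records the reason for leaving if known, and 13.5 reports the number of missing data. What is absent is all-cause mortality as an evaluation.
- *A subject who dies at day 90 has no tumor response.* An earlier category, including progression, remains an observed case at its own visit.
- *All tumor subjects are affected for EQ-5D.* EQ-5D is listed for liver but not for other hypervascular tumors.
- *The distortion must be large.* Fixing 12 responders among 30 subjects while deaths rise from 6 to 12 gives 12/24 = 50% to 12/18 = 67%, against 12/30 = 40%. That takes every death to be a non-responder, every survivor to be imaged and mortality to be 20% to 40%. None of these is in the documents.

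One objection to a simple repair also stands. Counting deaths as non-responders while still dropping survivors without imaging would give a mixed denominator. Imaging is done only if available, so that second group may not be small.

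A reader might also take the synopsis statement that primary endpoint data are collected at 30, 180 and 365 days to extend the death outcome. It does not, because the definition itself stops at 30 days. The two statements should be reconciled.

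**Conclusion.** The concern holds in a limited form. All-cause death after day 30 is not a listed evaluation, and 13.5 as written makes late tumor response (liver and other hypervascular tumors) and late EQ-5D (liver only) summaries of survivors with data. This affects how the 180- and 365-day tumor results are read. It does not touch the 30-day primary evaluations or responses recorded before death.

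The size cannot be derived from the documents. Across 5% to 40% mortality and 40% to 60% response among survivors, the observed-case rate exceeds the all-treated rate by about 2 to 24 percentage points, with all survivors assessed and death counted as non-response. At the low end this is minor. At the high end it would change the impression a reader takes away. It is worth settling before the analysis.

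**What to change.** 1. In Section 3.2.2 items 12 and 13, and in items 6 and 7 of the synopsis Procedure Evaluations, add all-cause mortality through day 365, estimated by Kaplan-Meier and censored at the last study contact date already defined in 13.2.1.
2. As a stated exception to 13.5, tabulate tumor response at each post-baseline visit over all treated tumor subjects, with separate rows for *died before assessment* and *alive, not assessed*. Give the response rate over all treated subjects beside the observed-case rate. The two rows keep deaths apart from absent imaging and avoid a mixed denominator. Synopsis item 7 omits the tumor response that Section 3.2.2 item 13 lists, so align the two at the same time.
3. Label late liver EQ-5D summaries as describing subjects alive and assessed, and show the number who died beside each. No score for death is needed.

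**Cost.** Protocol wording and one or two extra tables. Date of death and Kaplan-Meier are already in the plan. The documents describe no tracing of vital status after withdrawal or loss, so the mortality estimate will rest on censoring at last contact, and the report should say so. Late response rates over all treated subjects will be lower than the observed-case rates, partly because of deaths and partly because of survivors who were not imaged.

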4.1 Eligibility Criteria

4.1.1 Inclusion Criteria

Subject must meet all the following inclusion criteria to be enrolled in the study:

1. Subject is \geq 18 years old

2. Subject is scheduled for a procedure for treatment with HydroPearl microspheres using radial access.
3. Subject is willing and able to complete follow-up requirements
4. Subject is willing and able to sign a written Informed Consent form prior to participating in the registry.

4.1.2 Exclusion Criteria

Subjects will not be permitted to participate in the study if they meet any of the following exclusion criteria:

1. Unable to have a procedure with radial access for any reason.
2. Participating in another clinical study which, in the opinion of the investigator, could impact the results of this registry.
3. Pregnant or planning to become pregnant during the study.

4.2 Subject Enrollment

Up to 10 sites in the US and EU are expected to participate in the study with up to 100 subjects enrolled.

5 Ethics

5.1 Role of the Sponsor

The Sponsor has the overall responsibility for the conduct of the study, including assurance that the study meets all regulatory requirements. In this study, the Sponsor will have certain direct responsibilities and will delegate other responsibilities to the Clinical Research Organization (CRO). The Sponsor will conduct all its responsibilities in compliance with GCP and any applicable regulations.

5.2 Role of Clinical Research Organization

The Clinical Research Organization (CRO) will support the data management which includes, but is not limited to, informing the Sponsor of any unanticipated adverse device effects (UADEs) and serious adverse events (SAEs) as appropriate. The CRO will conduct all its responsibilities in compliance with the Code of Federal Regulations (CFR).

5.3 Ethics Review

The final study protocol and written Informed Consent Form must be approved in writing by an Institutional Review Board (IRB) and/or Ethics Committee (EC). The principal investigator is responsible for informing the IRB/EC of any amendments to the protocol in accordance with local requirements. In addition, if any advertising is used to recruit subjects to the study, the IRB/EC must approve prior to use. The protocol must be re-approved by the IRB/ EC annually, as local regulations require and where applicable.

Progress reports and notification of serious, unexpected adverse events will be provided to the IRB/EC according to local regulations and guidelines.

5.4 Ethical Conduct of the Study

The study will be performed in accordance with ethical principles that have their origin in the Declaration of Helsinki and are consistent with the ICH/GCP, ISO 14155 and MDR (EU) 2017/745. and applicable regulatory requirements.

5.5 Written Informed Consent

Written Informed Consent must be obtained prior to any study-related procedures*. The site principal investigator will ensure that proper informed consent is provided, including ensuring the subject is given full and adequate oral and written information about the nature, purpose, possible risks and benefits of the study. Subjects must also be notified that they are free to withdraw from the study at any time. The subject must be given the opportunity to ask questions and adequate time to consider the information provided. The site principal investigator will ensure that the subject has met all eligibility criteria prior to enrollment in the study.

The site principal investigator must store the original, signed written ICF per site specific procedures. A copy of the written ICF (paper or electronic) must be given to the subject. Any modifications made to the ICF must first be approved by the Sponsor and IRB/EC.

**Pre-procedure assessments considered standard of care completed prior to obtaining informed consent do not need to be repeated if performed within 90 days of the procedure unless the investigator feels it is medically necessary.*

5.6 Subject Data Protection

In accordance with the Health Information Portability and Accountability Act (HIPAA), the written Informed Consent Form must include a subject authorization to release medical information to the study Sponsor and/or allow the Sponsor or their designate, any regulatory authority, and IRB access to subject's medical information that includes all hospital records relevant to the study, including subjects' medical history.

In accordance with General Data Protection Regulation (EU) 2016/679 of the European Parliament and of the Council of 27 April 2016 on the protection of natural persons with regard to the processing of personal data and on the free movement of such data (General Data Protection Regulation), the written Informed Consent form must include a subject authorization to release medical information to the study Sponsor and or allow the Sponsor or their designate, a regulatory authority, or EC access to subject's medical information that includes all hospital records relevant to the study, including subjects' medical history.

To protect the patient's identity, a unique patient identification code will be assigned by the investigator to each trial patient and used instead of patient's name when the investigator reports adverse event and/or other trial related data. Thus, this number, rather than the patient's name, will appear on all documents and will be cross-referenced by the patient's date of birth. Personal information will be treated as confidential, but may need to be reviewed by the PIs, the ethics committee and regulatory authorities.

In order to be compliant with any country-specific laws, all relevant submissions, to the respective authorities will be done and the corresponding approval will be obtained before collection of any data considered to be sensitive, such as: ethnic origin, race, full date of birth etc

5.7 Subject Withdrawal

Subject participation in the study is voluntary. Subjects may withdraw their consent from participation in the study at any time. A subject may withdraw completely or may withdraw but leave the authorization to access their medical records in compliance with local regulations. Should a subject leave the study for any reason, the investigator will document the reason if known, and report in the study database.

5.8 Discontinuing Subject Participation

A subject's participation in the study may be terminated for the following reasons:

1. Serious or severe adverse event or unanticipated adverse device effect.
2. Termination of study by the Sponsor.
3. Investigator determination that continued participation is not in the best interest of the subject.
4. Subject withdrawal of consent at any time.

6 Device Supply Information

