7.6 Follow-up Procedures

Subjects will be evaluated prior to discharge, 30 days post-procedure, 180 days post-procedure, and 365 days post-procedure. All follow-up visit dates will be calculated based on a 30-day calendar.

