7.7 Clinical Data Collection

Information about subject demographics, eligibility requirements, procedure, specific concomitant medications as well as complications and/or device related adverse events will be collected on the eCRFs provided by the Sponsor. The eCRFs should accurately reflect data contained in the subject's medical records (i.e. source documents).

8 Adverse Events

Subject complications will be monitored via the reporting of device related adverse events occurring from the time of enrollment (insertion of guidewire into radial artery) through study completion (withdrawal for any reason or completion of 365-day follow-up visit). For this registry, adverse events collected will be limited to any events possibly, probably or definitely related to a Terumo device, as described below in Section 8.2.

Where an adverse event has, by its nature, a prolonged course, the event will be considered a single event and not multiple events.

The investigator is not required to actively seek adverse events from a subject once a subject has exited the study. If the investigator learns of any device related adverse event at

any time after a subject's exit from the study, the investigator should promptly report it to the Sponsor.

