8.3 Follow-up of Adverse Events

All device related adverse events observed from the time of enrollment throughout the duration of the study must be reported on the eCRF. All device related adverse events will be followed until resolution or stabilization of symptoms through study completion and/or the subject withdraws consent. Resolution means that the subject has returned to a baseline state of health. Stabilization means that the investigator does not expect any further improvement or worsening of the adverse event.

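### Section 5.8 lets registry follow-up end because of a serious or severe adverse event, so under observed-case analysis the late (180- and 365-day) results can be missing for reasons tied to outcome

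*Combined protocol and SAP*

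**What the plan says.** Section 5.8 (Discontinuing Subject Participation) opens with "A subject's participation in the study may be terminated for the following reasons", and its first reason is "Serious or severe adverse event or unanticipated adverse device effect". The reason is not limited to device-related events. Reasons 3 and 4 separately cover the investigator's judgement of the subject's best interest and withdrawal of consent.

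Follow-up is meant to be complete. Section 2.3 states "Follow-up will continue for each subject through 365-days post-procedure", and Section 7.6 states "Subjects will be evaluated prior to discharge, 30 days post-procedure, 180 days post-procedure, and 365 days post-procedure".

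On events, Section 8.3 states "All device related adverse events will be followed until resolution or stabilization of symptoms through study completion", with withdrawal of consent as a further end point. Section 8 defines the end of event reporting as "study completion (withdrawal for any reason or completion of 365-day follow-up visit". It limits collection to device-related events and does not oblige the investigator to look for events after exit.

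On missing data, Section 13.5 states "The number of missing data will be reported" and "Only observed cases will be considered". It gives no imputation, no sensitivity analysis and no rule for subjects who leave after an adverse event.

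**The concern.** In a trial with continuing treatment, a rule of this kind usually stops exposure. Here the index procedure is a single event on Day 0 (Section 13.2.1), with commercial product used on-label (Section 6.1). Ending participation afterwards takes away no study-imposed exposure. It only stops the data.

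The trigger is itself a poor outcome. Subjects removed on this ground plausibly have worse later quality of life, symptoms or tumour response than those who stay, and the analysis then describes only those who stay. Kaplan-Meier summaries (Section 13.2) would not repair this, because censoring at such an exit would be informative. Section 13.7 also makes study success depend on minimal missing data, and this exit ground creates missing data that could be avoided.

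At stake is possible bias in descriptive late estimates, plus the later course of some events. No hypothesis is tested, so error rates and power are not at issue.

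**Working it through.** **The plan's own figure.** The only calculation in the plan is in Section 13.1: 100 evaluable patients and a 1.6% rate. The probability of seeing at least one major complication is 1 − (1 − 0.016)^100 = 0.8007, which agrees with the stated figure of more than 80%. It is not in dispute and is used below only as a source for the 1.6% rate.

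**Is the data lost after a Section 5.8 exit recovered anywhere?**

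- Section 5.7 lets a subject who withdraws leave access to medical records in place. Section 5.8 does not extend this to subjects who are terminated.
- Section 5.7 has the reason for leaving recorded if known. No analysis uses it.
- Section 8 asks the investigator to report a device event learned of after exit, but not to seek one.
- Section 8.3 follows device-related events only to study completion or withdrawal of consent. Whether a Section 5.8 termination is a withdrawal in the sense of Section 8 is not stated. If it is, the event that triggers the exit also closes its own follow-up. If it is not, the definition of study completion does not cover the terminated subject.
- A serious or severe event judged unrelated to the device can trigger exit under Section 5.8 but is not collected under Section 8. It would appear only as an exit reason.

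So no section requires late data after such an exit.

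**Size for a continuous outcome.** Let p be the share removed and d the amount by which their mean is worse than that of the subjects who stay, whose mean is m. The full mean is (1 − p)m + p(m − d) = m − pd. The observed-case mean is m. The bias is therefore p × d.

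The documents give neither p nor d. Assume d = 0.3 on the EQ-5D index. For p, take the documents' two major complication rates as low values (0.13% from the large retrospective series in Section 1; 1.6% from Section 13.1) and 5% to 10% as assumed high values.

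- p = 0.0013: 0.0013 × 0.3 = 0.0004
- p = 0.016: 0.016 × 0.3 = 0.0048, about 0.005
- p = 0.05: 0.05 × 0.3 = 0.015
- p = 0.10: 0.10 × 0.3 = 0.03
- d = 0: the bias is zero for any p

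The low values are not estimates of p. The trigger also takes in severe events unrelated to the device, which could make p larger. The rule is optional, which could make p smaller.

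**Size for a yes/no outcome.** With k of 100 removed, a poor-outcome rate q in them and r in the rest, the observed rate is r and the understatement is k(q − r)/100. Assume r = 10% and q = 50% to 100%.

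- k = 2: full rate 10.8% to 11.8%, understated by 0.8 to 1.8 points
- k = 5: full rate 12.0% to 14.5%, understated by 2.0 to 4.5 points
- k = 10: full rate 14.0% to 19.0%, understated by 4.0 to 9.0 points
- q = r: no understatement

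**The case against.** The strongest reply is that the rule is permissive and may seldom be used, and that several safeguards exist: exit reasons are recorded, device events learned of later are to be reported, and reported device events go through the manufacturer's usual process (Section 8.6). At the documents' own complication rates the bias is negligible. Other missing data may well be larger: at 30 and 180 days only the quality of life questionnaire is required, and imaging is collected if available. All of this stands, and it limits the size of the point. None of it requires follow-up after exit, so the point itself remains.

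A reader might infer more than the text supports:

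- *That late results will look better than they are.* The text supports only that they can. Nothing directs sites to use reason 1, and the bias is zero if those removed do no worse.
- *That Section 8 plainly contradicts Section 8.3.* Section 8.3 is itself bounded by study completion or consent withdrawal. Section 5.7 uses withdrawal for the subject's own act, while Section 5.8 speaks of termination. This is an ambiguity to reconcile, not a settled conflict.
- *That access-complication and primary results are distorted.* A device-related complication that prompts the exit has already been recorded, so only later events are lost. Procedural and technical success are determined at the procedure. The 30-day safety evaluation would be affected only by a termination before that visit.
- *That the course of the event is lost in every such subject.* On one reading of Sections 8 and 8.3, follow-up of a device event continues.

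**Conclusion.** The point holds in limited form. The plan permits an exit tied to outcome that serves no evident purpose in a registry of a completed procedure, sets no requirement to collect data afterwards, and analyses only what was observed. The exposed results are late quality of life, symptoms and tumour response, and any later device events.

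The documents do not determine the size. On the assumed EQ-5D deficit it runs from about 0.0004 to 0.03 across removal of 0.13% to 10%. For a yes/no outcome it is 0.8 to 9.0 percentage points across 2 to 10 removals per 100 when those removed do clearly worse. Both fall to zero if they do not. No sample-size figure changes. The change is worth making because it is cheap, not because a large bias has been shown.

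**What to change.** These changes concern data collection only, not the subject's care.

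1. Delete reason 1 from Section 5.8 as a ground for ending follow-up. Reasons 3 and 4 remain to protect the subject.
2. State that subjects with a serious, severe or unanticipated event, and those discontinued under reason 3 where consent remains, stay in follow-up to day 365 by visit, telephone or record review unless they withdraw consent. Without the reason 3 clause, the same exit would stay open by another route.
3. Reconcile the end-of-reporting definition in Section 8 with Sections 8.3 and 5.7, so that an open device event is still followed where record access remains.
4. In Section 13.5, add a tabulation of missing 180- and 365-day data by exit reason.

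The cost is protocol wording, one table and a few extra telephone or chart contacts. Those contacts are not all in the present schedule, since Section 7.6 provides for telephone follow-up only at day 365.
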